## 3. ANALYSIS SETS

**Table 3 Analysis sets**

Analysis Set	Definition / Criteria	Analyses Evaluated
Enrolled	Participants who agreed to participate in a clinical study after completion of the informed consent process	Study Population
Exposed	All Participants who received at least 1 dose of the study treatment. The allocation in a group is done as a function of the administered treatment	Safety, Study Population
Full Analysis Set (FAS)	All Participants who received at least 1 dose of the study intervention and have post-vaccination immunogenicity data  It will be defined by timepoint, e.g. FAS at Day 31	Immunogenicity
Per-Protocol Set (PPS)	All Participants who received at least 1 dose of the study treatment to which they are randomized and have post-vaccination data minus participants with protocol deviations that lead to exclusion  It will be defined by timepoint, e.g. PPS at Day 31	Immunogenicity
Solicited Safety Set	All Participants who received at least 1 dose of the study intervention (Exposed Set) who have solicited safety data	Solicited events
Randomized Set	Randomized set will include all participants who are randomized. The allocation in a group is done as function of the randomized intervention. Please note this set was not included in the protocol, but will be used later in one summary analysis, so it is added here for clarification.	Disposition

### 3.1. Criteria for eliminating data from Analysis Sets

Elimination codes are used to identify participants to be eliminated from analysis. Detail is provided below for each set.

#### 3.1.1. Elimination from Exposed Set (ES)

Code 1030 (Study vaccine not administered at all), 800 (Fraudulent data) and code 900 (invalid informed consent) will be used for identifying participants eliminated from ES

#### 3.1.2. Elimination from Full Analysis Set (FAS)

A participant will be excluded from the FAS under the following conditions

**Table 4** Elimination code and condition

Code	Condition under which the code is used	Visit (timepoints) where the code is applicable	Applicable for analysis set/endpoint
800	Fraudulent data	All	All
900	Invalid informed consent	All	All
1030	Study vaccine not administered at all	All	Safety, immunogenicity
2100.Vx	Serological results not available post-vaccination	Visit 2/Day 31	Immunogenicity

Vx indicates participants whose immunogenicity data will be eliminated from a specific visit.

#### 3.1.3. Elimination from Per-protocol Set (PPS)

A participant will be excluded from the PPS under the following conditions

**Table 5** Elimination code and condition

Code	Condition under which the code is used	Visit (timepoints) where the code is applicable	Applicable for analysis set/endpoint
800	Fraudulent data	All	All
900	Invalid informed consent	All	All
1030	Study vaccine not administered at all	All	Safety, immunogenicity
1040.Vx*	Administration of concomitant vaccine(s) forbidden in the protocol	Visit 2/Day 31	Immunogenicity
1050	Randomisation failure	All	Immunogenicity
1060	Randomisation code was broken	All	Immunogenicity

Code	Condition under which the code is used	Visit (timepoints) where the code is applicable	Applicable for analysis set/endpoint
1070**	Subjects got vaccinated with the correct vaccine but containing an incorrect volume	All	Immunogenicity
1070**	Vaccination not according to protocol (site of injection, route of administration, wrong replacement of study treatment administered)	All	Immunogenicity
1070**	Study treatment not prepared as per protocol (e.g., reconstitution)	All	Immunogenicity
1070**	Other deviations related to wrong study treatment/administration/dose	All	Immunogenicity
1070**	Study treatment administered while contraindication	All	Immunogenicity
1080	Vaccine temperature deviation	All	Immunogenicity
1090	Expired vaccine administered	All	Immunogenicity
2010	Protocol violation (inclusion/exclusion criteria) DOB – VAC – 18-49 years BMI <=40 kg/m 	All	Immunogenicity
2040.Vx*	Administration of any medication forbidden by the protocol	Visit 2/Day 31	Immunogenicity
2050.Vx*	Intercurrent medical conditions which are exclusionary as per protocol	Visit 2/Day 31	Immunogenicity
2090.Vx	Subjects did not comply with blood sample schedule: 

For PPS at Day 31, check the interval from vaccination to day 31 BS = 31 – 38 days;

	Visit 2/Day 31	Immunogenicity
2100.Vx	Serological results not available post-vaccination	Visit 2/Day 31	Immunogenicity
2120.Vx	Obvious incoherence or abnormality or error in data	All	Immunogenicity
2130.Vx	Testing performed on samples not aligned with ICF	All	Immunogenicity

\*Attribution of these elimination codes to subject need CRDL review of individual listing

\*\* Attribution of code 1070 to a subject requires CRDL confirmation

Vx+ indicates participants whose immunogenicity data will be eliminated from a specific visit onwards; Vx indicates participants whose immunogenicity data will be eliminated from a specific visit.

DOB-Date of Birth, VAC-Vaccination, BS- Blood Sample, BMI-Body Mass Index.

### **3.1.4. Elimination from solicited safety set**

Code 1030 (Study vaccine not administered at all), code 800 (fraudulent data) and code 900 (invalid informed consent) and code 1160 (no post-vaccination solicited safety data) will be used for identifying participants eliminated from the solicited safety set.

## **4. STATISTICAL ANALYSES**

### **4.1. General Considerations**

Unless otherwise specified, reactogenicity analysis and safety analysis will be performed on solicited safety set and Exposed Set respectively. Immunogenicity analysis will be performed on the Per Protocol set and may be performed on the Full Analysis Set if necessary.

#### **4.1.1. General Methodology**

Unless otherwise specified, continuous data will be summarized using descriptive statistics: n, mean, standard deviation (std), median, minimum and maximum. Categorical data will be summarized as the number and percentage of participants in each category.

95% CI for proportion will be based on exact Clopper-Pearson confidence interval [[Clopper](#), 1934].

95% CI for group difference in proportion will be based on Miettinen and Nurminen confidence interval [[Miettinen](#), 1985].

95% CI for GMT(C) will be based on a back transformation of student confidence interval for the mean of log-transformation.

95% CI for GMT(C) ratio between groups will be based on a back transformation of confidence interval for the mean difference on log-transformation.

For a given participant and given immunogenicity measurement, missing or non-evaluable measurements will neither be imputed nor be replaced, and therefore will not be included in immunogenicity analysis.

For between group statistical modelling analysis, participants having a result at both the baseline and the considered timepoint will be included in the analysis.

Participants who prematurely withdrew from study will not be replaced.

#### **4.1.2. Definition**

Solicited events and their intensity scales are defined as below:

CCI - This section contained Clinical Outcome Assessment data collection questionnaires or indices, which are protected by third party copyright laws and therefore have been excluded.

Baseline: For all endpoints the baseline value will be the latest pre-dose assessment with a non-missing value, including those from unscheduled visits. If time is not collected, Day 1 assessments are assumed to be taken prior to vaccination and used as baseline. Unless otherwise stated, if baseline data is missing no derivation will be performed and baseline will be set to missing.

For the RSV and FLU antigens:

- A seronegative participant will be defined as a participant whose antibody titer/concentration is below the cut-off value of the assay.
- A seropositive participant is a participant whose antibody titer/concentration is greater than or equal to the cut-off value of the assay.
- MGI (mean geometric increase): The geometric mean of the within participant ratios of the post-dose titer over the pre-dose titer.

Please refer to Section [6.2.4.6](#) for cut-off value for each assay.

For the FLU antigens:

- SCR (seroconversion rate): The percentage of participants who have either a HI pre-dose titer < 1:10 and a post-dose titer  $\geq 1:40$  or a pre-dose titer  $\geq 1:10$  and at least a four-fold increase in post-dose titer.
- SPR (seroprotection rate): The percentage of participants with a serum HI titer  $\geq 1:40$  that usually is accepted as indicating protection.

## **4.2. Primary Endpoint(s) Analyses**

### **4.2.1. Safety analysis**

The analysis of solicited administration site event (associated with RSV or Flu) and solicited systemic event will be performed on solicited safety set.

- The number and percentage with exact 95% CI of participants reporting each solicited administration site event (any grade, each grade) and solicited systemic event (any, each grade) during the 7-day follow-up period after dosing will be tabulated by maximum intensity per participant for each study group.
- For fever during the 7-day follow-up period after vaccination, the number and percentage of participants reporting any fever (i.e., temperature  $\geq 38$  °C) and fever by half degree (°C) cumulative increments, any Grade 3 fevers, will be reported.
- Duration in days of solicited administration site and systemic events within 7 days after vaccination will be tabulated by study group and overall. The derivation rule of duration in days for solicited events is detailed in section [6.2.4.9](#).

The analysis of unsolicited AEs and SAEs will be performed on ES.

- The number and percentage of participants reporting unsolicited AEs within 30 days after dosing with exact 95% CIs will be tabulated by group and by Medical Dictionary for Regulatory Activities (MedDRA) terms.
- Similar tabulations will be done for Grade 3 unsolicited AEs, for any causally related unsolicited AEs, and for Grade 3 related unsolicited AEs.
- The number and percentage of participants reporting at least one SAE within 30 days after dosing with exact 95% CIs will be tabulated by group and by MedDRA terms.
- The number and percentage of participants reporting at least one SAE up to study end with exact 95% CIs will be tabulated by group and by MedDRA terms.
- By-participant listings of SAEs, and AEs leading to study withdrawal will be prepared.

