# 3. OBJECTIVE(S), ENDPOINTS, AND ESTIMANDS (Amended 26 May 2022)

# Table 3 Study objectives, endpoints and estimands

	Objectives	Endpoints/Estimands				
	Primary					
•	To evaluate the safety and reactogenicity of RSVPreF3 when given alone (pooled lots) or co- administered with Flu D-QIV up to study end .	
 
The number and percentage of participants in each group reporting
 
Each solicited administration site AE collected during the 7 days follow-up period (Day 1 to Day 7)
 
Each solicited systemic events in the 7 days follow-up period
 
Unsolicited AEs collected during the 30 days follow-up period (Day 1 to Day 30)
 
SAEs in the 30 days follow-up period (Day 1 to Day 30)
 
				
		• SAEs in the 180 days follow-up period (Day 1 to Day 181)				
lmmı	unogenicity	RSVPreF3 IgG ELISA concentration at Day 31 (30 days				
•	To demonstrate the lot-to-lot consistency of 3 lots of the investigational RSVPreF3 vaccine based on GMC of RSVPreF3 IgG ELISA at Day 31	Measured by ratio of Geometric mean concentration (GMC) between lots in terms of RSVPreF3 IgG ELISA titers at Day 31 (30 days post administration)				
•	To demonstrate non-inferiority of Flu D-QIV vaccine when co-administered with RSVPreF3 vaccine compared to Flu D-QIV given alone based on Geometric mean titer (GMT) of Flu D-QIV antibody titers against 3 influenza strains at Day 31 post administration	Flu D-QIV antibody titers against 3 influenza strains at Day 31 (30 days post administration) Measured by ratio of Haemagglutinin inhibition (HI) GMT between group of Flu D-QIV vaccine co-administered with RSVPreF3 vaccine and Flu D-QIV vaccine alone group against 3 strains at Day 31 (30 days post administration)				
	Secondary					
	Confirmatory In	nmunogenicity***				
•	To demonstrate the non-inferiority of RSVPreF3 vaccine co-administered with Flu D-QIV compared to given alone based on GMT of RSV A neutralizing antibody at Day 31 post administration	RSV A neutralizing antibody titers at Day 31 (30 days post administration) Measured by ratio of GMT between group of RSVPreF3 vaccine co-administered with Flu D-QIV and RSVPreF3 vaccine alone (pooled lot 1,2,3) group in term of RSV A neutralizing antibody titers at Day 31 (30 days administration)				

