# 4.2. Scientific rationale for study design

This study is part of a clinical development plan of the RSVPreF3 vaccine for the protection of infants from RSV lower respiratory tract infections through maternal immunization. This study will evaluate the safety and immunogenicity of the RSVPreF3 vaccine from 3 lots as well as when co-administered with GSK quadrivalent influenza (Flu D-QIV) vaccine in healthy non-pregnant women 18-49 YOA.

To evaluate lot-to-lot consistency, 3 groups will be vaccinated with 3 different lots. RSV1 vs. RSV2, RSV 2 vs. RSV 3, and RSV3 vs. RSV1 will be compared. An optional Flu D-QIV will be provided to these three groups during Visit 2 as part of the standard of care. To evaluate the impact of co-administration on the flu immunogenicity, the safety and immunogenicity of the Flu + P and Flu + RSV groups will be compared. The study will also evaluate the impact of co-administration on RSVPreF3 immunogenicity; by comparing the immunogenicity of pooled RSV1,2,3 group versus RSV+Flu group. Blood samples for humoral immune response will be collected on Day 1(Vaccination day) and Day 31 (Visit 2).

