# 6.3.5. Blinding and unblinding

Data will be collected in an observer-blind manner to evaluate the lot-to-lot consistency of GSK RSVPreF3 vaccine and single-blind manner to evaluate the immune response, safety and reactogenicity of RSV maternal vaccine when co-administered with GSK quadrivalent influenza. To do so, study interventions will be prepared and administered by qualified study personnel who will NOT participate in data collection, evaluation, review or the entry of any study endpoint (i.e. reactogenicity, safety, immunogenicity).

- This study will utilize an observer-blind design as described below:
  - For the Lot-to-Lot consistency groups (RSV1, RSV2, and RSV3), both the participant and investigator will be blinded to the lot received. However, they will both know that the participant is not part of the co-administration study groups.
- This study will utilize a single blind design as described below:
  - For the co-administration groups (Flu+RSV or Flu+P), the investigator and participant will both know that the participant is part of the co-administration study groups. However, the participant will be blinded to the vaccine administration activities. Participant will be administered with either RSVPreF3 or Flu D-QIV on the left arm. On the right arm, participant will be administered with either Flu D-QIV or the placebo.
- This blinding strategy will apply from Visit 1 to *study end (Day 181) (Amended 26 May 2022)*.

The laboratory in charge of sample testing will be blinded to the study intervention assignment. Codes will be used to link the participant and study to each sample. There will be no link between the study intervention and the identity of the participant.

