Source documents:	Original legible documents, data, and records (e.g. hospital records, clinical and office charts, laboratory notes, memoranda, participants' diaries or evaluation checklists, pharmacy dispensing records, recorded data from automated instruments, copies or transcriptions certified after verification as being accurate copies, microfiches, photographic negatives, microfilm or magnetic media, x-rays, participant files, and records kept at the pharmacy, laboratories and at medico- technical departments involved in the clinical trial).

Study intervention:	Any investigational or marketed product(s) or placebo intended to be administered to a participant during the study.	
Unsolicited adverse event	Any AE reported in addition to those solicited during the clinical study. Also, any 'solicited' symptom with onset outside the specified period of follow-up for solicited symptoms will be reported as an unsolicited adverse event	

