### 1.1. Objectives, Estimands and Endpoints

**Table 1 Study objectives, endpoints and estimands**

Objectives	Endpoints/Estimands
Primary	
Safety	
The number and percentage of participants in each group reporting
 
 
• Each solicited administration site AE collected during the 7 days follow-up period (Day 1 to Day 7)
 
• Each solicited systemic events in the 7 days follow-up period
 
• Unsolicited AEs collected during the 30 days follow-up period (Day 1 to Day 30)
 
• SAEs in the 30 days follow-up period (Day 1 to Day 30)
 
• SAEs in the 180 days follow-up period (Day 1 to Day 181)
 

Immunogenicity	
RSVPreF3 IgG ELISA concentration at Day 31 (30 days post administration)
 
Measured by ratio of Geometric mean concentration (GMC) between lots in terms of RSVPreF3 IgG ELISA titers at Day 31 (30 days post administration)
 
Flu D-QIV antibody titers against 3 influenza strains at Day 31 (30 days post administration)
 
Measured by ratio of Haemagglutinin inhibition (HI) GMT between group of Flu D-QIV vaccine co-administered with RSVPreF3 vaccine and Flu D-QIV vaccine alone group against 3 strains at Day 31 (30 days post administration)

Secondary	
Confirmatory Immunogenicity**	

 
• To demonstrate the non-inferiority of RSVPreF3 vaccine co-administered with Flu D-QIV compared to given alone based on GMT of RSV A neutralizing antibody at Day 31 post administration
 
• To demonstrate the non-inferiority of Flu D-QIV vaccine co-administered with RSVPreF3 compared to given alone based on Seroconversion rate (SCR*) of Flu D-QIV HI antibody titers against 3 influenza strains at Day 31 post study intervention
 
	
RSV A neutralizing antibody titers at Day 31 (30 days post administration)
 
Measured by ratio of GMT between group of RSVPreF3 vaccine co-administered with Flu D-QIV and RSVPreF3 vaccine alone (pooled lot 1,2,3) group in term of RSV A neutralizing antibody titers at Day 31 (30 days administration)
 
 
• Seroconversion rate to Flu D-QIV HI antibody titers against the 3 influenza strains at Day 31
 
 
Measured by the difference of proportion of participants achieving seroconversion for HI antibody at Day 31 in the group of Flu D-QIV vaccine co-administered with

Objectives	Endpoints/Estimands

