#### **4.7. Changes to Protocol Defined Analyses**

There were no changes or deviations to the planned statistical analysis specified in the protocol amendment 3 (Dated: [26-MAY-2022]).

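### SAP 4.2.1 ties the local-reaction analysis to RSV and Flu, so on its natural reading saline-site reactions in Flu+P drop out of a primary endpoint that has no product limit

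*SAP*

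**What the plan says.** The current SAP (Amendment 2) introduces the local-reaction analysis in section 4.2.1 with "The analysis of solicited administration site event (associated with RSV or Flu) and solicited systemic event will be performed on solicited safety set". The same parenthetical stands in section 4.2.1 of both earlier SAP versions. The bullet beneath it has no product limit: percentages with exact 95% intervals "will be tabulated by maximum intensity per participant for each study group".

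The endpoint itself is unrestricted. SAP Table 1 has, per group, "Each solicited administration site AE collected during the 7 days follow-up period (Day 1 to Day 7"), and protocol Table 3 and protocol 9.4.1 match it.

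Each woman in Flu+P has two injection sites. Protocol Table 6 puts Flu D-QIV in the left arm and placebo in the right. For the co-administration groups, protocol 6.3.5 says: "On the right arm, participant will be administered with either Flu D-QIV or the placebo". The protocol glossary (10.8.2) defines a study intervention as "Any investigational or marketed product(s) or placebo intended to be administered to a participant during the study", so saline counts as one.

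Two other SAP sections bear on the point. Section 6.2.4.10 counts the same local event after several study interventions once per participant. Section 4.7 states: "There were no changes or deviations to the planned statistical analysis specified in the protocol amendment 3".

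**The concern.** The parenthetical narrows a primary endpoint that the protocol leaves unrestricted, and the narrowing is not declared. A Flu+P woman whose only local reaction is at the saline site meets the endpoint in both documents. A programmer who follows the opening sentence of SAP 4.2.1 would not count her.

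At stake is how the RSV+Flu and Flu+P columns can be read together. Protocol 4.2 says "the safety and immunogenicity of the Flu + P and Flu + RSV groups will be compared", and readers will set the two columns side by side even though the analysis is descriptive. Saline is the trial's only inert injection, so its site shows the background of local reactions to an injection as such. If any-site percentages are shown with saline left out, one group is counted over two injections and the other over one. Part of the difference then comes from the number of sites counted, not from RSVPreF3.

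**Working it through.** **Stated figures.** The documents give no site-specific reaction rate, so there is none to reproduce. The nearest stated figures are the safety-precision values in protocol 9.2.4 and Table 18 for 440 participants:

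- Chance of at least one event at a true rate of 1%: 1 - 0.99^440 = 0.988, matching the stated 98.8%.
- Exact upper limit with no events: 1 - 0.025^(1/440) = 0.0083, matching 0.83%.

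All eight rows of Table 18 also reproduce. They depend on 440 and 660 participants, not on which sites are counted, so this point changes none of them.

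**The text, side by side.**

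| Source | Product limit on local events? | Saline site in Flu+P |
|---|---|---|
| Protocol Table 3, protocol 9.4.1, SAP Table 1 | None | Counted |
| SAP 4.2.1, opening sentence | RSV or Flu | Left out on the natural reading |
| SAP 4.2.1, first bullet | None | Counted |
| SAP 6.2.4.10 with the protocol glossary | None; placebo is a study intervention | Counted, once per event |
| SAP 4.7 | Declares no change | No support for leaving it out |

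The parenthetical is unlikely to refer to causality, because protocol 10.3.9.2 asks for causality only for unsolicited AEs and SAEs. Reference to the injection site is the more plausible meaning.

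**Size in an any-site table.** Let f be the Flu-site rate, q the saline-site rate and r the RSVPreF3-site rate, with sites independent.

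- RSV+Flu, any site: 1 - (1 - r)(1 - f).
- Flu+P with saline left out: f.
- Flu+P as the endpoint defines it: 1 - (1 - f)(1 - q).
- Inflation of the RSV+Flu minus Flu+P gap: [1 - (1 - f)(1 - q)] - f = (1 - f)q. The RSV+Flu term cancels, so r does not matter.

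Assumed rates, none of them from the documents:

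| f | q | Flu+P, saline left out | Flu+P, saline counted | Inflation (points) |
|---|---|---|---|---|
| 30% | 5% | 30% | 33.5% | 3.5 |
| 30% | 20% | 30% | 44% | 14 |
| 45% | 5% | 45% | 47.75% | 2.75 |
| 45% | 20% | 45% | 56% | 11 |

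At f = 40%, the women affected would be 440 x 0.60 x q: about 13 at q = 5%, 26 at 10% and 53 at 20%.

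**Wider range and dependence.** For f from 20% to 60% and q from 5% to 20%, independence gives 0.40 x 0.05 = 2 points to 0.80 x 0.20 = 16 points. Without independence, the inflation is the share of women who react at the saline site but not at the Flu site. Over these rates it runs from 0 (full overlap) to q, so at most 20 points (no overlap). Positive within-woman correlation, which is plausible, pulls it towards 0.

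**The case against.** The strongest reply is that the SAP contains no exclusion rule. The parenthetical sits in a sentence whose purpose is to name the analysis set. The operative bullet, SAP Table 1 and the counting rule in 6.2.4.10 are all unrestricted, and the elimination criteria in SAP section 3.1 say nothing about placebo sites. The phrase may simply mean that tables are split by product. In that case no any-site figure arises and there is no inflation. This stands as a possible reading, and for that reason exclusion is put here as the natural reading and not as an established fact. It does not remove the need for a correction, because two programmers could build different Flu+P columns for a primary endpoint. The SAP version history also records that allocation in the co-administration groups could be worked out from the eCRF, which is a reason to settle the choice in writing.

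A second reply is that nothing confirmatory is affected. The primary safety objective is to evaluate RSVPreF3 alone or with Flu D-QIV, protocol 8.2 makes the safety analysis descriptive, and no contrast with the placebo site is planned. The comparison sentence in protocol 4.2 opens with the effect on influenza immunogenicity. Any error would overstate RSVPreF3 local reactogenicity and so would not hide a signal. All of this stands and limits the weight of the point.

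Two stronger inferences are tempting and do not hold:

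- **That saline is the only blinded control injection.** Under protocol 6.3.5 the participant is equally masked to the left-arm injection, RSVPreF3 or Flu D-QIV, and Flu-site events in Flu+P stay in the analysis. Saline is the only inert injection. Masking in these groups is of the participant only.
- **That saline-site events appear nowhere.** SAP 4.5.1 plans a combined solicited and unsolicited summary for registry posting, with no RSV or Flu limit. It codes to general injection-site terms, so it would not show saline-site rates separately. If it includes them, posted figures could differ from the 4.2.1 table.

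**Conclusion.** The point holds as an undeclared mismatch between the SAP's description of the analysis and the primary endpoint. On its natural reading, SAP 4.2.1 leaves saline-site reactions in Flu+P out of the local-reactogenicity table. The endpoint includes them, and SAP 4.7 records no change.

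The numerical consequence is conditional. It arises only if saline is left out and any-site rates are tabulated. The 3 to 14 points is an illustration that rests on assumed Flu-site rates of 30-45%, assumed saline-site rates of 5-20% and independent sites; it is not an estimate for this trial. A reader might infer that a planned comparison or test is biased. The documents do not support that: the safety analysis is descriptive, and no confirmatory result or stated precision figure moves. The SAP should still be corrected before the tables are produced, because the endpoint is primary and the correction is small.

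**What to change.** In SAP 4.2.1, replace the parenthetical with *at each injection site (RSVPreF3, Flu D-QIV or placebo)*. Tabulate local events by site and product, including the placebo site in Flu+P. If an any-site percentage is also shown, count the placebo site for Flu+P. If RSVPreF3-site rates in RSV+Flu are set beside placebo-site rates in Flu+P, note that the injections are in opposite arms. If leaving saline out is intended, declare it as a change in SAP 4.7 and give the reason.

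The cost is one phrase and one extra table column, assuming the e-diary records local events by injection site. Protocol 10.3.8 says only that the diary captures administration-site events, so that should be confirmed first.
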